#### **Experiences of using NHS patient medicines helplines**

to them. Planned and spontaneous prompts will also be used to encourage participants to describe their experiences in greater depth.

Two interviews schedules were developed in order to collect slightly different data from patients and carers. For the carer interview, the patient whom the carer cares for has not consented to participate in this study, nor have they consented for their medication and health-related information to be disclosed. Although the main topics for the two interviews are the same, the use of probes has been restricted for certain questions in the carer interview schedule (e.g., the question about the impact that the use of the helpline service has had). For carers, there is no need to probe for information regarding the patient's medication use and health status, since the emphasis of their interview is upon whether or not, as a carer, their needs were met when using the helpline service.

The development of the interview schedules were informed by the following sources: relevant research, including a systematic review of the impact of patients medicines helplines (44), and a survey study of how patient medicines helplines are currently operated in England (40); UK national standards for operating a patient medicines helpline (43); the RE-AIM and APEASE criteria for evaluating interventions (71); the Sekhon et al. framework of the acceptability of healthcare interventions (70); and the Delorme et al. model of medicines information-seeking behaviour (97). Table 1 outlines the topics for the interviews.

The interview schedules were developed with the involvement of two relevant groups:

1. People who have recently been discharged from hospital, or carers of people who have recently been discharged from hospital (see section 8.6 Patient and Public Involvement).
2. Pharmacy professionals with expertise in Medicines Information and operating a patient medicines helpline.

Individuals who helped develop the data collection tools will be excluded from participating in the actual study.

Table 1. Topics for the interviews with service users

Topics for interviews with service users
1. Why the patient/carer contacted the helpline service, including what their question or concern was, the perceived seriousness of the issue, whether they considered any other sources of medicines information, and their decision-making process for choosing to use the helpline service.
2. What the patient/carer found helpful and unhelpful about their experience of contacting the medicines helpline service.
3. What impact the patient's/carer's use of the service has had (e.g., Was the advice followed? If so, what were the outcomes of this? If the advice was not followed, what were the reasons for this?).
4. Whether there were any self-perceived negative consequences of using the helpline service.
5. How the patient/carer feels about the medicines now, compared to before the helpline contact.
6. How the patient/carer feels about the hospital and NHS Trust now, compared to before the helpline contact.
7. What the patient/carer would have done had the helpline service not been available, or if the helpline service was not local, and why.
8. Whether the patient/carer sought any other sources of medicines-related information or support following their use of the helpline service, and if so, why.

#### **5.2.4 Demographics questionnaire**

The following demographic data will be collected directly after the semi-structured interviews using a data collection form: Age; gender; ethnicity; occupational status; current occupation (if applicable); highest educational qualification attained. We will also ask participants for their email address or postal address, for the purpose of sending them their £10 voucher for taking part in the study.

#### **5.2.5 Call log**

Sites will be asked to keep a log of calls received during the recruitment period. An excel document has been created for this purpose. The data to be logged will be anonymous, and will comprise the following: Date and time of the call; caller ID number; whether or not the caller was told about the study; if the caller was not told about the study, the reason why not (e.g., not meeting the eligibility criteria); if the caller was told about the study, whether or not they agreed to receive the information sheet; whether the information sheet has been sent. The caller ID number will be the unique ID number allocated to enquirers in MiDatabank, the national system which is used to record, manage and store enquiries used by MI teams in the UK. This number will be used so that pharmacy professionals can keep track of who calls and whether or not they have been sent an information sheet, while ensuring that the call log is anonymous to the research team.

## 5.3 Procedure

Data collection will take place within one month of service users' contact with a medicines helpline service. However, ideally data will be collected as soon as possible after the helpline contact. This is to increase the chance that the caller will remember their experience of using the service, during their interview. Data collection will occur at one time-point, over the telephone, and will involve the consent process, answering background information questions pertaining to the helpline call, participating in a semi-structured interview, and answering demographic questions. Overall, the entire telephone call will last approximately 20-30 minutes.

### 5.3.1 Consent

Prior to participating in the study, all participants must consent to taking part. Since data will be collected via the telephone, consent will also be obtained verbally, over the telephone.

In order to establish that the individual has capacity to participate in the study, prior to consent, they will be asked to briefly describe what the study involves, based upon the information they have received about the study. If they are unable to accurately describe what the study entails, they will be informed that they unfortunately do not meet the criteria for participating in the study, and thanked for their interest. Individuals who are able to accurately describe what the study entails will be asked to consent to participate as long as they meet all of the study inclusion/exclusion criteria, as outlined in Section 7.1).

The British Psychological Society (BPS) propose that "The way in which consent is sought from people to participate in or otherwise contribute data for research should be appropriate to the research topic and design" ((113), pg 15). The BPS state that consent via verbal recording is acceptable, provided there is an explicit statement confirming that the participant has received information about the research and the information has been understood (113). This research study is considered to be low risk, since the aim is to examine service users' experiences of using a medicines helpline service. For such a study design, it would be advantageous to collect data as soon as possible after the helpline contact has taken place, to facilitate the recounting of participants' experiences. Additionally, data will be collected via telephone interview rather than face-to-face. Collecting written consent will likely increase the number of days between the helpline contact and the interview, compared to a verbal recording of consent. Therefore, a verbal recording of consent is deemed to be appropriate for this low risk, telephone interview study.

A script has been developed to facilitate the telephone call with service users, and to ensure that the information which participants receive at the start of the call is standardised. At the start of the telephone call, the participant will be asked if they agree for the call to be audio-recorded. Consent to take part in the study will involve MW reading out all consent statements in the consent form over the telephone and asking the participant if they agree to each statement. The consent statements have been informed by the consent preparation guidance of the Health Research Authority (112), and the University of Bath Research Ethics Approval Committee for Health (117). The statements are:

- 1) Please could you confirm that you have received information about the study, that you have had the opportunity to consider the information, ask questions about the study, and have had these answered satisfactorily?
- 2) Do you understand that your participation is voluntary and that you are free to withdraw from the study at any time without giving a reason, without your medical care or legal rights being affected?
- 3) Do you understand that your anonymised data may be retained for at least 10 years in accordance with the University of Bath Research Data Policy, and that it may be shared and used to support other research in the future?
- 4) Do you understand that parts of your interview may be used verbatim in future publications or presentations and that such quotes will be anonymised (i.e., they will not mention you personally)?

5) Do you understand that if you disclose any thoughts or actions of harm to yourself during this interview, that it is our duty to inform the Pharmacy team at the NHS Trust where you received care, so that they can inform your GP?

6) Do you agree to take part in the study?

The consent process will take approximately 5 minutes. The audio recording for the consent process will be separate from the recording for the interview, to ensure that the interview recording, including the file name, can be anonymised. Prior to the interview, participants will also be made aware that the research is independent of the hospital at which they were admitted, thereby encouraging participants to disclose their experiences of the helpline service, whether positive or negative.

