## **1.6 Effectiveness of patient medicines helplines**

Since the primary aim of patient medicines helpline services are to provide service users with information and support with their medicines (30), their effectiveness could be assessed in terms of whether or not they achieve this from the perspectives of the service user. Effectiveness could also be assessed in terms of whether or not the impact of the information/support upon the service user is perceived to be positive.

Service evaluation studies have sought to examine the proportion of service users who feel that they have a greater understanding of their medicines as a result of contacting a patient medicines helpline. Surveys of helpline users have found that between 62% and 82% of respondents reported that they had an improved understanding of their medicines following their helpline interaction (77-79). This suggests that between 18% and 38% of respondents either understood their medicines to the same level as before, or felt less of an understanding as a result of the helpline interaction. However, such findings are limited by being based upon single survey items. It could be that, despite efforts by the pharmacy team to provide clarification, some service users may remain feeling confused about aspects of their medication after contacting the helpline. There is an assumption that their knowledge gap is filled as a result of using the helpline service, and that service users understand the information and advice they receive. However, evidence is needed to ascertain this.

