To date, no qualitative research has been published which explores service user experiences of contacting a medicines helpline. Such a design would be unique, and would be suited to explore patients' understanding and knowledge of the information or advice they have received. This is important, given that research shows that patients often lack knowledge of their medicines following hospital discharge (10, 13, 80) and that clinicians may overestimate patients' understanding of treatment consultations (81, 82). It is therefore feasible that patients may come away from the helpline interaction with ongoing knowledge gaps. Qualitative methods would be suitable for asking the question 'How do service users make sense of the information and advice provided by the pharmacist?'. Qualitative methods would also provide service users with an opportunity to describe any ongoing lack of understanding or confusion they may have regarding their medicines.

Service evaluation survey studies suggest that between 88% and 97% of service users reported following the advice they received (33, 35, 77, 79). However, one study reported that 96% of service

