Sites will be involved in the recruitment of participants. At the end of helpline calls, the pharmacy professional who dealt with the enquiry will ask the caller whether they would be interested in receiving information about the study. If so, the pharmacy professional will send an invite letter and Participant Information Sheet to the caller. The letter and information sheet will be sent by the NHS Trust, and the letter will be printed on NHS Trust headed paper. This will happen for all callers who meet the study inclusion/exclusion criteria, detailed in Section 7.1. Therefore, the pharmacy professional will ascertain whether or not each caller meets the study inclusion/exclusion criteria in order to know whether or not to ask the caller about the study.

The research team at the University of Bath will not have access to any patient information. The

Participant Information Sheet informs potential participants to contact the research team if they would like to participate, or if they have any questions about the study. The research team will only hear about the individual if the individual contacts the research team to express an interest in taking part in the study. The Participant Information Sheet also informs potential participants that the telephone interview should ideally be conducted as soon as possible after their contact with the helpline service (and within one month). This is to attempt to minimise memory errors of their accounts of their experiences.

Research suggests that approximately 70% of calls to patient medicines helplines are from patients and 30% of calls are from carers (30). Therefore, both patients and carers will be invited to participate in this study. However, we will not strategically select individuals to ensure that the sample consists of both patients and carers. All individuals who express an interest in participating, and who meet the study inclusion/exclusion criteria, will be invited to participate. MW will liaise with participating sites to ensure that recruitment stops once 30 participants have been interviewed (or until data saturation has been reached, if this has not occurred by the 30th interview). This will reduce the likelihood that helpline callers will be sent information about the study when the recruitment phase has ended.

Participants will not be recruited by any other methods (e.g., publicity, posters, leaflets, adverts or websites).

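### The capacity check in Section 5.3.1 excludes a volunteer after one inaccurate description of the study, with no re-explanation, no second attempt and no count of those excluded

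*Protocol*

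**What the plan says.** Section 5.3.1 gives the purpose of the check as capacity: "In order to establish that the individual has capacity to participate in the study, prior to consent". The task is one open request: "they will be asked to briefly describe what the study involves, based upon the information they have received about the study". The consequence of failing is stated outright: "If they are unable to accurately describe what the study entails, they will be informed that they unfortunately do not meet the criteria". The person is then thanked. Those who pass go on to consent, provided they also meet the Section 7.1 criteria.

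The same section mentions a call script, one purpose of which is "to ensure that the information which participants receive at the start of the call is standardised". It does not say whether that information includes a summary of the study, or whether it comes before or after the check. The first consent statement, put to those who have passed, asks them to confirm that they could "ask questions about the study, and have had these answered satisfactorily". Section 7.3.1 gives an earlier route: the information sheet tells people to contact the research team if they want to take part "or if they have any questions about the study".

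On why understanding matters, Section 1.6 says that "some service users may remain feeling confused about aspects of their medication after contacting the helpline", and later: "It is therefore feasible that patients may come away from the helpline interaction with ongoing knowledge gaps". Section 8.1 adds that interviewees will describe how they understood the advice they were given, and that some may have misunderstood it.

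**The concern.** A capacity check should separate people who can understand and decide from people who cannot. A rule that ends the process at the first inaccurate answer also removes people who would have understood after a short explanation. The protocol does not say how accurate the description must be, so the line depends on the interviewer's judgement.

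Two things are at stake. Volunteers who could consent may be turned away from a study that the protocol itself regards as low risk. And the sample may contain fewer people who have difficulty with information they are given. Accounts of continuing confusion or misunderstood advice are one of the stated reasons for using interviews rather than surveys. If fewer of them are heard, the themes may lean towards the view that helplines meet information needs, which Section 2 calls an assumption that still needs evidence. Because nobody is asked to count these exclusions, a reader of the results could not judge how far this happened.

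**Working it through.** The protocol gives no figure for failures at this step, so the check is mainly a comparison of sections. The arithmetic only sets bounds.

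**1. The rule against the criterion it serves.** Section 7.1.3 requires ability and willingness to give informed consent. It does not list an accurate description of the study, and Section 5.3.1 treats the description as a condition alongside the Section 7.1 criteria. The description is therefore a measuring tool for ability to consent. One answer, with no attempt to correct it, cannot distinguish inability from a sheet read quickly or some time ago.

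**2. The rule against the aims.** Sections 1.6 and 8.1 want accounts from people who remained confused or misunderstood. The check selects on describing information received. The two may overlap, but the protocol offers no measure of the overlap.

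**3. Whether the loss would be visible.** The log in Section 5.2.5 records who was told about the study, who agreed to receive the sheet and whether it was sent. Section 7.3.1 uses the site figures to work out the proportion of callers who decide to participate. A willing volunteer turned away at the check would be counted with those who did not take part. Section 8.1 concedes selection bias only for site screening, on the grounds that inviting some callers might cause distress and that sites would not otherwise join. Neither ground applies to a check run by the research team.

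**4. Does it threaten the number of interviews?** Inputs: 5 calls per Trust per week, six months (26 weeks) and a 37% response rate (Section 7.2.1); at least two Trusts (Section 6).

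- Expected respondents = 5 × 26 × 2 × 0.37 = 96.2.
- Failure fraction at which 30 interviews become unreachable = 1 − 30/96.2 = 0.69.
- This treats every call as eligible and invited. Even with an assumed 20% failing, 96.2 × 0.80 = 77.0 remain, and 30/77.0 = 0.39, so 30 is reached if at least 39% of calls lead to an invitation.

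**5. How many might be turned away?** Volunteers needed for 30 interviews = 30/(1 − f), where f is an assumed failure fraction.

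- f = 0.05: 30/0.95 = 31.6, about 2 turned away.
- f = 0.20: 30/0.80 = 37.5, about 8 turned away.

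**6. How far could composition shift?** Let p be the share of responders with poor understanding and q the assumed chance that they fail; assume others never fail. Their share after the check is p(1 − q)/(1 − pq). For p, take the 18% to 38% of survey respondents in Section 1.6 who did not report improved understanding. Expected number among 30:

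| q (assumed) | p = 0.18 | p = 0.38 |
|---|---|---|
| 0 | 5.4 | 11.4 |
| 0.25 | 4.2 | 9.4 |
| 0.50 | 3.0 | 7.0 |
| 0.75 | 1.6 | 4.0 |
| 1 | 0 | 0 |

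Example: p = 0.18, q = 0.5 gives 0.09/0.91 = 0.099, and 30 × 0.099 = 3.0. The protocol supplies no value for q, so the table shows only that the effect could run from nothing to substantial.

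**The case against.** The strongest reply is that this is an ordinary capacity safeguard and the selection effect is conjecture. Describing a single telephone interview is a much simpler task than understanding medicines advice. The sheet was developed with patients, carers and pharmacy professionals, and public reviewers commented on its clarity (Sections 5.2.1 and 8.6.2). Section 8.1 plans for participants who have misunderstood advice, so the protocol expects such people in the sample. The study seeks themes from a purposive sample and does not estimate how often needs are met. A pilot and a paper trail are promised (Sections 5.3.5 and 5.3.7), and nothing prevents the team from keeping a count.

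Much of this stands, and it rules out several stronger readings. A reader might infer an unprompted memory test. The text does not bar consulting the sheet, and the scripted information may come before the check. A reader might infer that questions can be asked only after the check, but Section 7.3.1 gives an earlier route. A reader might infer that the study was set up chiefly to explore poor understanding, but the research question in Section 4.1 is experiences in general, and understanding is one strand.

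What the reply does not remove is the rule itself. As written, one inaccurate description leads to exclusion, no standard of accuracy is given, and neither the pilot nor the paper trail commits to a count of those excluded.

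**Conclusion.** The point holds as an avoidable and uncounted selection risk. The exclusion after one inaccurate description is an explicit rule, and it is a weak measure of ability to consent. It may under-represent callers with poor understanding. The size is unknown: the failure rates and values of q above are assumptions, and the protocol gives no link between understanding medicines advice and describing this study. The documents therefore do not support saying that the check screens such people out, that those turned away would all come from this group, or that the findings will overstate how well helplines work. The planned 30 interviews are not at risk under the protocol's own inputs. The change is worth making because it is cheap and keeps the safeguard.

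**What to change.** Amend Section 5.3.1 and the call script so that, if the first description is incomplete or inaccurate, the interviewer explains the study using the existing script, answers questions and asks again. Exclude only those who still cannot describe it. State briefly what an adequate description must contain. Have the research team record the number excluded at this step and report it alongside the site call-log figures.

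The cost is one to two extra minutes on some calls, a short script edit and a protocol amendment, with no extra staff or participants. The consent time should be restated in the same amendment, since Section 5.3.1 allows about 5 minutes and Section 8.1 allows 1 to 2.

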### **5.3.2 Collecting background information pertaining to the helpline call and participants' background**

Following consent, service users will be asked to answer questions pertaining to the background of the helpline call, in order to add context to the sample in the study write-up (see Section 5.2.2 for information about what data will be collected). This process will take approximately 5 minutes.

